4.4.2. Handling of missing values in scales or summary parameters

Missing items in scales or summary parameters will be imputed to allow for the derivation of the total scale/parameter score. The appropriate imputation rules will be described in the sections where the total scores are defined.

4.4.3. Handling of missing values and early dropouts in the efficacy analyses during the first study period (up to Week 12)

This is for the “efficacy chapter 2” analysis.

For binary data (e.g., ACR20), two different imputations will be done for missing visits as well as early dropouts: non-responder imputation (NRI) and LOCF, up to and including Week 12. The NRI imputation will be primary, and LOCF will be secondary.

For other data (ordinal or continuous), missing visits as well as early dropouts will be imputed using the last observation carried forward (LOCF) algorithm, up to and including Week 12.

Definitions of the imputation methods:

- LOCF (all types of parameters, from binary to continuous): to impute a missing value, the last preceding nonmissing value will be used (which could even be a baseline value).
- NRI (binary response parameters only): to impute a missing response, the subject will be assumed to be a non-responder.

For all parameters, an observed-case analysis will also be performed (i.e., without any imputation). The observed-case analysis will serve as a sensitivity analysis (to ascertain the impact of early dropouts on the results) and will basically be limited to:

- ACR20/50/70/N: descriptive at W12+W24 and inferential at W12
- EULAR remission: descriptive at W12+W24
- SDAI/CDAI: descriptive at BSL+W12+W24
- DAS28: descriptive at BSL+W12+W24 and inferential at W12
- All ACR components (VAS, joint counts, CRP, HAQ-DI): descriptive at BSL+W12+W24
- QoL (FACIT,SF-36): descriptive at BSL+W12+W24.

4.4.4. Handling of missing values and early dropouts in the efficacy analyses during the study period as a whole (full 24 weeks)

This is for the “efficacy chapter 2” analysis.

For binary data (e.g., ACR20), two different imputations will be done for missing visits as well as early dropouts: non-responder imputation (NRI) and LOCF, up to and including Week 24. The NRI imputation will be primary, and LOCF will be secondary.

For other data (ordinal or continuous), missing visits as well as early dropouts will be imputed using the last observation carried forward (LOCF) algorithm, up to and including Week 24.

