6.1.2.3. Methods of analysis

Efficacy data (ACR20, ACR50, ACR70, ACR-N, DAS28(CRP), EULAR response, and ACR/EULAR remission, and components of the ACR, CDAI and SDAI at each post dosing visit) will be analyzed descriptively.

The efficacy analysis will present the results in 2 chapters:

1. Chapter 2: Analysis of the full 24 weeks study period.
2. Chapter 3: Analysis of the second study period, from Week 12 onwards.

All chapters will use the original baseline visit as reference.

Handling of discontinued subjects during the 24 weeks treatment period:

- Subjects who discontinue within the first week so that ACR20/50/70 responses cannot be determined will be classified as non-responders.
- For all discontinued subjects, visits after their discontinuation will be imputed for a duration depending on the analysis chapter:
 - Chapter 2: subjects discontinuing during the first study period will have their remaining visits imputed up to and including Week 12.
 - Chapter 2: subjects discontinuing the study will be imputed up to and including Week 24, irrespective of whether they discontinued during the first or second study period.
 - Chapter 3: subjects discontinuing during the first study period will not be imputed during the second study period. Subjects discontinuing during the second study period will be imputed up to and including Week 24.

The method of imputation will depend on the parameter: NRI and LOCF for binary data; LOCF for ordinal or continuous data. Observed-case will always be presented as well.

All non-responding subjects from the lowest dose group who are re-randomized at Week 12 will be handled as follows, again depending on the analysis chapter:

- Chapter 2: their original treatment group of the first study period will be used. The Week 12 value will be carried forward to all further time points (and between-group comparisons) after Week 12.
- Chapter 3: their actual assessments on Weeks 16-20-24 will be analyzed descriptively using the new treatment groups.
- See also: overview table, section 2.1.

All placebo subjects switch to 100 mg q.d. at Week 12. As a result, no placebo group will be available during the second part of the study (chapters 2 and 3).

Between-group comparisons will be done for each dose group versus the placebo group (up to Week 12; not after Week 12). Hommel's closed-testing correction procedure (as implemented in SAS PROC MULTTEST) will be applied to adjust for multiplicity.

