8.4.2. Tables over the whole 24 weeks period

Tables will present Baseline-Weeks 1-2-4-8-12-16-20-24, unless specified otherwise. Tables will present the imputed 4 treatment groups up to Week 12, and leave out the placebo group after Week 12, as mentioned in section 2.1.1.

A similar analysis as to SDAI and CDAI will be performed. Analysis population: ITT. LOCF and observed case (descriptive at baseline, week 12 and week 24; inferential statistics only at Week 12).

Table 14.2.1.4.1: DAS28(CRP): Descriptive statistics of the actual values

(descriptive statistics, including a frequency table)

Analysis population: ITT and per-protocol.

Table to be created for the Week 12 interim analysis as well, cut off at Week 12. ITT only.

Table 14.2.1.4.2: DAS28(CRP): Descriptive statistics of the change from baseline

(descriptive statistics, including a shift table)

Analysis population: ITT and per-protocol.

Table to be created for the Week 12 interim analysis as well, cut off at Week 12. ITT only.

Table 14.2.1.4.3: DAS28(CRP): Descriptive statistics of the percent change from baseline

(descriptive statistics, including a frequency table at weeks 12 + 24)

Analysis population: ITT and per-protocol.

Table to be created for the Week 12 interim analysis as well, cut off at Week 12. ITT only.

Table 14.2.1.4.4: DAS28(CRP): Summary with overall p-value and pairwise comparisons versus placebo

Analysis population: ITT and per-protocol.

Table to be created for the Week 12 interim analysis as well, cut off at Week 12. ITT only.

Table 14.2.1.4.5: DAS28(CRP): Exploratory pairwise comparisons among the dose groups

Analysis population: ITT and per-protocol.

Table to be created for the Week 12 interim analysis as well, cut off at Week 12. ITT only.

Table 14.2.1.4.6: DAS28(CRP) change from baseline at Week 12: Tabulation versus baseline characteristics

The table will show LOCF only.

Descriptive statistics of the DAS28(CRP) change from baseline at Week 12 per treatment group, split up according to the following baseline categories:

- Demographics:
 - Region (as used in the central randomization)
 - Country
 - Gender
 - Age categories:
 - < 45 ;
 - [45,65[;
 - [65,75[;
 - ≥ 75 years
 - BMI categories:
 - ≤ 18.5;
 -] 18.5 , 25.0] ;
 -] 25 , 30 [,
 - ≥ 30 kg/m²
- Baseline disease characteristics:
 - Duration of RA:
 - < 1;
 - [1 , 2 [;
 - [2 , 5 [;
 - [5 , 10 [;
 - [10 , 20 [;
 - ≥ 20 years
 - Baseline CRP:
 - <0.7 x ULN;
 - [0.7,1.0] x ULN;
 -]1.0,1.2[x ULN;

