 - ≥ 1.2 x ULN
 - Baseline TJC68: < 20, ≥ 20
 - Baseline SJC66: < 20, ≥ 20
 - Baseline DAS28(CRP): high, moderate, low, remission (see further section on DAS28 for the definition of these categories)
 - RF status
 - Anti-CCP status
 - Previous use of:
 - Biological DMARD (anti-TNF or other biological DMARD) yes/no
 - anti-TNF yes/no,
 - other biological DMARD yes/no,
 - conventional DMARD yes/no,
 - NSAID yes/no,
 - steroid yes/no,
 - analgesic yes/no,
 - other RA medication yes/no.

Population: ITT.

Table 14.2.1.4.7: DAS28(CRP) change from baseline at Week 12: Exploratory ANCOVA model containing baseline characteristics

The table will show LOCF only.

ANCOVA model of the DAS28(CRP) change from baseline at Week 12, with the following exploratory factors:

- Treatment group
- Demographics:
 - Region
 - Country
 - Gender
 - Age as continuous variable
 - BMI as continuous variable
- Baseline disease characteristics:
 - Duration of RA as continuous variable
 - Baseline CRP as continuous variable
 - Baseline TJC68 and SJC66 as continuous variables
 - Baseline DAS28(CRP) as continuous variable
 - RF status
 - anti-CCP status
 - Previous use of:
 - Biological DMARD (anti-TNF or other biological DMARD) yes/no
 - anti-TNF yes/no,
 - other biological DMARD yes/no,
 - conventional DMARD yes/no,
 - NSAID yes/no,
 - steroid yes/no,
 - analgesic yes/no,
 - other RA medication yes/no.

All these factors will be tested using a stepwise selection approach. Significance level to enter the model: 0.10; significance level to stay in the model: 0.05. The treatment groups will always be kept in the model, even when not significant at level 0.05. The table will present only the final model with type-III p-value and LS-mean estimates. The “raw” SAS PROC output must be provided in a statistical appendix listing, and will contain all details on the model building steps.

Population: ITT.

Table 14.2.1.4.8: DAS28(CRP) remission: Summary with overall p-value and pairwise comparisons versus placebo

Similar table as for ACR20, presenting the rates of DAS28(CRP) remission at Week 12 and Week 24.

The table will show:

- NRI in ITT
- LOCF in ITT
- observed-case in ITT (descriptive at Week 12 + 24; inferential statistics at Week 12 only).

Table 14.2.1.4.9: DAS28(CRP) remission: Exploratory pairwise comparisons among the dose groups

Table 14.2.1.4.10: DAS28(CRP) remission and low disease activity: Summary with overall p-value and pairwise comparisons versus placebo

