Similar table as for the remission, but now combining “remission” and “low disease activity” into one percentage.

Table 14.2.1.4.11: DAS28(CRP) remission and low disease activity: Exploratory pairwise comparisons among the dose groups

Table 14.2.1.4.12: DAS28(CRP) EULAR response: Frequency table

Frequency per time point, and per treatment group. EULAR response will be presented in the categories defined above (none, moderate, good).

Overall p-value and pairwise comparisons versus placebo: Cochran-Mantel-Haenszel test for row mean score differences, controlling for region and prior biologics. These p-values will be corrected for multiplicity according to Hommel’s closed-testing method as implemented in SAS PROC MULTTEST. The uncorrected p-values will also be presented.

Population: ITT and per-protocol.

Table 14.2.1.4.13: DAS28(CRP) EULAR response: Exploratory pairwise comparisons among the dose groups

Analysis population: ITT and per-protocol.

Comparisons between the doses: Cochran-Mantel-Haenszel test for row mean score differences, controlling for region and prior biologics. As this is purely exploratory, no correction for multiplicity will be done.

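### EULAR response, a secondary responder endpoint with multiplicity-corrected tests, has no planned analysis that counts subjects who leave before Week 12 as failures

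*SAP*

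**What the plan says.** SAP 4.4.3 provides two imputations for binary data such as ACR20 and ranks them: "The NRI imputation will be primary, and LOCF will be secondary". The scope of NRI is explicit: "NRI (binary response parameters only): to impute a missing response, the subject will be assumed to be a non-responder". Everything else goes to LOCF: "For other data (ordinal or continuous), missing visits as well as early dropouts will be imputed using the last observation carried forward (LOCF) algorithm". SAP 6.1.2.3 repeats the split: "NRI and LOCF for binary data; LOCF for ordinal or continuous data. Observed-case will always be presented as well".

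EULAR response falls on the LOCF side. SAP 8.4.1 derives it from DAS28(CRP) in three ordered categories. Its table entry (14.2.1.4.12) names no imputation. The introduction to SAP 8.4.2, which covers it, names "LOCF and observed case (descriptive at baseline, week 12 and week 24; inferential statistics only at Week 12". The entry prescribes a Cochran-Mantel-Haenszel (CMH) row-mean-score test controlling for region and prior biologics, with Hommel-corrected comparisons against placebo.

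The binary endpoints built from the same score are treated differently. Table 14.2.1.4.8 is described as "Similar table as for ACR20, presenting the rates of DAS28(CRP) remission at Week 12 and Week 24" and is to be shown under NRI, LOCF and observed case. Table 14.2.1.4.10 (remission plus low disease activity, that is DAS28(CRP) ≤ 3.2) follows the same format. ACR20/50/70, ACR/EULAR remission and SDAI/CDAI remission also have NRI versions.

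Protocol 6.6 describes the EULAR criteria as sorting subjects into non-responders, moderate responders and good responders. The synopsis lists EULAR response as a secondary endpoint.

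**The concern.** EULAR response has a defined failure level (None), so NRI could be applied to it without any new concept. It is left out because the rule asks whether a variable is binary, not whether it measures response.

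As a result, one subject can be classed in two ways at the same visit. Someone whose last assessment is at Week 4, and who is Good then, fails at Week 12 for ACR20 and for DAS28(CRP) ≤ 3.2 under the primary imputation, yet counts as a Week 12 Good responder in Table 14.2.1.4.12. Leaving while responding is plausible: protocol 8.3.4 lists infection and laboratory grounds for withdrawal that do not depend on efficacy, and protocol 8.5.7 withdraws unblinded subjects.

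What is at stake is how a tested secondary result reads beside the other response endpoints.

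**Working it through.** **The plan's own figures.** The documents state no figure for EULAR response. The arm size of 70 comes from protocol 8.8.2. Its ACR20 power reproduces with a pooled chi-square test at two-sided alpha 5%/3: 90.7% (15% v 43%), 89.1% (40% v 70%), 79.8% (15% v 39%) and 80.0% (40% v 67%), against the stated 90%, 90%, 80% and 80%. So 70 is a sound denominator.

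**Who is affected.** SAP 3.3 gives the Week 12 window as days 71 to 98 and allocates early discontinuation visits by day. The issue concerns subjects with no DAS28(CRP) in that window whose last earlier category was Good or Moderate.

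**Effect per subject.** 1/70 = 1.43 percentage points of that arm's Week 12 rate.

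**Effect per arm (assumed inputs).** Added rate = dropout fraction × share Good or Moderate at the last visit. The documents give neither. For 5% to 15% dropout and a share of 30% to 60%, the range is 0.05 × 0.30 = 1.5 points to 0.15 × 0.60 = 9 points.

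**Effect on the treatment difference.** This is the dose-arm amount minus the placebo-arm amount. Over the same ranges it runs from 1.5 − 9 = −7.5 to 9 − 1.5 = +7.5 points, and is zero when the two amounts are equal. The sign is not determined.

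**Nesting.** Good requires DAS28(CRP) ≤ 3.2 and improvement > 1.2, so it is a subset of DAS28(CRP) ≤ 3.2. In one arm, let C be the number observed at Week 12 with DAS28(CRP) ≤ 3.2, G the number of those who are Good, and k the number of dropouts carried forward as Good.

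- NRI rate of DAS28(CRP) ≤ 3.2: C/70
- LOCF rate of Good: (G + k)/70
- LOCF rate of DAS28(CRP) ≤ 3.2: at least (C + k)/70

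LOCF Good exceeds NRI DAS28(CRP) ≤ 3.2 exactly when k > C − G. It can never exceed LOCF DAS28(CRP) ≤ 3.2.

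**Illustration (assumed counts).** 70 subjects, 7 dropouts, C = 20, G = 19, k = 3:

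| Week 12 rate | NRI | LOCF | Observed case |
|---|---|---|---|
| Good | 19/70 = 27.1% (not planned) | 22/70 = 31.4% | 19/63 = 30.2% |
| DAS28(CRP) ≤ 3.2 | 20/70 = 28.6% | at least 23/70 = 32.9% | 20/63 = 31.7% |

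Each column is in the right order. The reversal appears only across columns: 31.4% for Good (LOCF) against 28.6% for the set containing it (NRI).

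**How easily it arises.** Subjects counted in C − G need a baseline DAS28(CRP) of at most 3.2 + 1.2 = 4.4. By the SAP formula, TJC28 = 8, SJC28 = 6, CRP 6.3 mg/L (0.7 × 8.999) and an assumed patient global of 50 mm give 4.65 (4.23 at 20 mm, 4.93 at 70 mm). Eligibility uses the 68- and 66-joint counts, so the 28-joint counts can be lower: 6 and 4 at 50 mm give 4.31. The group is probably small but need not be empty. With C − G = 0, one dropout carried as Good produces the reversal; with C − G = 1, two are needed.

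**Observed case.** SAP 4.2 removes missing values from the denominator, so observed case omits dropouts instead of counting them as failures.

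**The case against.** The case for leaving the plan alone has real content.

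- **It follows the protocol.** Protocol 8.8.1.3 plans LOCF for discontinued subjects, and EULAR response is a second categorization of DAS28(CRP), itself a LOCF endpoint. This stands: there is no contradiction between protocol and SAP.
- **A like-for-like comparator exists.** A reader might infer that the plan can report a logically impossible order. It cannot do so within one imputation, and the LOCF table of DAS28(CRP) ≤ 3.2 is already planned. This stands. The mismatch arises only when the LOCF EULAR table is read beside the NRI version that the SAP ranks first.
- **EULAR response is not alone.** A reader might infer that it is the only response measure without NRI. HAQ-DI ≤ 0.5, CRP normalization and the SDAI/CDAI activity categories also lack it. Those tabulations are descriptive, so the statement holds only for named responder endpoints with between-group tests.
- **The carried value is often recent.** Discontinuing subjects have an early discontinuation visit with the needed assessments, so LOCF often carries the state at exit. True, but that subject is still a failure under NRI elsewhere.
- **Sensitivity analysis is planned.** Observed case is planned, but it does not count dropouts as failures, so it does not fill the gap.
- **Consequence is limited.** EULAR response is secondary, in an exploratory dose-finding study, and is not in the interim efficacy list. This stands and limits the weight of the point.

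**Conclusion.** The gap is real and modest. No planned analysis of EULAR response treats a subject who leaves before Week 12 as a failure, while the other named responder endpoints with between-group tests all have one and rank it first. Each dropout carried forward as Good or Moderate adds 1.4 points to that arm's rate. The per-arm range of 1.5 to 9 points rests wholly on assumed dropout and response-at-exit figures.

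A reader might infer that the comparison with placebo is biased in favour of GLPG0634. The documents do not support that: LOCF acts in every arm, and the direction depends on which arm loses more responders. Nor does the point require NRI to be the truth; it asks for the SAP's own rule for response endpoints to be applied to this one. That the three-level scale is the reason is inferred from the general rule, since the EULAR response table entry names no imputation.

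This is a worthwhile, inexpensive improvement. The primary ACR20 analysis and the sample size are unaffected.

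**What to change.** In SAP 4.4.3 and Tables 14.2.1.4.12 and 14.2.1.4.13, add an NRI analysis of EULAR response at time points up to Week 12, with a missing response set to None, and run the same CMH row-mean-score tests. Present it first, as for the other response endpoints. Keep LOCF (as in protocol 8.8.1.3) and observed case alongside. Good then cannot exceed DAS28(CRP) ≤ 3.2 when both are read under the leading imputation.

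After Week 12, apply it only to true dropouts and missing visits. SAP 4.5.1 treats 50 mg subjects who switch as discontinued, while SAP 6.1.2.3 carries their Week 12 value forward. The switch depends on SJC66 and TJC68, so a switcher can be Moderate at Week 12, and blanket NRI would turn that subject into None. Leave the carry-forward for switchers as it is.

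The cost is SAP wording, one more run of existing tables and slightly lower reported EULAR response rates. A dropout may also appear in remission in the LOCF DAS28(CRP) categories of Table 14.2.1.4.1 and as None in the new version, so label the imputation on each table.

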### **8.8.2 Determination of Sample Size**

The sample size calculation is based on the expected ACR20 response rates at Week 12.

Assuming:

- 4 treatment arms with an equal (1:1:1:1) group allocation, and
- n=70 in each of the study arms, with a total of N=280 in the study, and
- Alpha = 5%/3 = 1.67% per comparison versus placebo, and
- a 15% to 40% placebo ACR20 response at Week 12.

Then the study has 90% power to detect a 28% (=43% - 15%) to 30% (=70% - 40%) treatment difference versus placebo, depending on the placebo response rate. This is considered clinically meaningful.

The study also has 80% power to detect a 24% (=39% - 15%) to 27% (=67% - 40%) treatment difference versus placebo, depending on the placebo response rate.

Calculations were performed using a chi-square approach in nQuery 7.0.

Note that the type-I error rate was Bonferroni-adjusted for the 3 comparisons versus the placebo group. No further correction of the type-I error rate is required for the Week 12 interim analysis because it matches the primary efficacy analysis (ACR20 at Week 12).

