This study is not powered for any formal comparison among the dose groups. However, differences among the q.d. groups will be calculated and presented with a 95% confidence interval (all time points, also after Week 12). No adjustment for multiplicity will be done for these exploratory differences.

Analysis methods per post-baseline time point:

- Binary parameters (such as ACR20): logistic regression model with factors treatment, region and previous use of biologics.
- Continuous parameters: both the changes from baseline and the percent changes from baseline will be described. Formal between-group comparisons will be performed on the changes from baseline only, using an analysis of (co)variance (AN[C]OVA) model with factors treatment, baseline value, region and previous use of biologics. Baseline will be the last nonmissing value prior to first dosing in the study.
- Time to (first) response (ACR20/50/70) will be analyzed using Kaplan-Meier survival techniques, and groups will be compared against placebo using a Cox proportional hazards regression model with factors treatment, region and previous use of biologics.

Quality of Life data (FACIT fatigue scale and SF-36 questionnaire) will be analyzed descriptively. Exploratory between-group comparisons will also be done at each post-baseline time point using AN(C)OVA models on the changes from baseline with factors treatment, baseline value, region and previous use of biologics.

A descriptive sensitivity analysis by baseline characteristic (such as country, geographic region, previous use of biological DMARDs etc) will be performed for the ACR20 response and the change in DAS28(CRP). Additionally an exploratory regression model will be fitted using a stepwise selection algorithm on the ACR20 response and the change in DAS28(CRP) at Week 12, using treatment and baseline characteristics as explanatory factors to investigate which baseline factors have an influence on the response.

Graphical presentations are added to facilitate the overall interpretation of the study results.

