8.3.2. Tables over the whole 24 weeks period

Tables will present Baseline - Weeks 1-2-4-8-12-16-20-24, unless specified otherwise. Tables will present the imputed 4 treatment groups up to Week 12, and leave out the placebo group after Week 12, as mentioned in section 2.1.1.

Analysis population: ITT. LOCF and observed case (descriptive only).

Table 14.2.1.3.1: SDAI and CDAI: Descriptive statistics of the actual values

Descriptive statistics of the actual values per time point, and per treatment group.

Frequency per time point, and per treatment group. SDAI and CDAI will be presented in the categories defined above (remission, low, moderate, high).

The table will show:

- LOCF in ITT
- observed-case in ITT (Baseline, Week 12 and Week 24 only)

Table 14.2.1.3.2: SDAI and CDAI: Descriptive statistics of the change from baseline

Descriptive statistics of the changes from baseline per time point, and per treatment group.

The table will show:

- LOCF in ITT
- observed-case in ITT (weeks 12 + 24 only)

Table 14.2.1.3.3: SDAI and CDAI: Descriptive statistics of the percent change from baseline

Descriptive statistics of the percent changes from baseline per time point, and per treatment group.

Frequency table at Weeks 12 and 24 with cumulative percentages of the percent change from baseline, categorized as:

≥ 0 ,
 [-10 , 0 [,
 [-20 , -10 [,
 [-30 , -20 [,
 [-40 , -30 [,
 [-50 , -40 [,
 [-60 , -50 [,
 [-70 , -60 [,
 [-80 , -70 [,
 [-90 , -80 [,
 [-100 , -90 [.

The table will show:

- LOCF in ITT
- observed-case in ITT (weeks 12 + 24 only)

Table 14.2.1.3.4: SDAI and CDAI: Summary with overall p-value and pairwise comparisons versus placebo

ANCOVA model on the change from baseline at each time point. Factors in the model are: treatment, baseline value, region, and previous use of biologics.

Per time point, the table will present:

- Overall type-III p-value for all explanatory factors in the model.
- Per group: difference in LS-means versus the placebo group (GLPG0634 minus placebo), together with a 95% confidence interval of this difference.
- Per group: p-value for pairwise comparison versus the placebo group, derived from contrasts within the overall model. These p-values will be presented both as uncorrected p-values as well as corrected for multiplicity according to Hommel's closed-testing method (SAS PROC MULTTEST).

The "raw" SAS PROC output must be provided in a statistical appendix listing.

The table will show:

- LOCF in ITT

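### For most continuous secondary endpoints the only test is run on LOCF data, so the plan cannot show whether those conclusions depend on the imputation

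*SAP*

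**What the plan says.** SAP 4.4.3 imputes all ordinal and continuous efficacy data by LOCF up to Week 12, both for missed visits and for dropouts. A missing value is replaced so that "the last preceding nonmissing value will be used (which could even be a baseline value"). SAP 6.1.2.3 then compares groups on change from baseline at each time point, "using an analysis of (co)variance (AN[C]OVA) model with factors treatment, baseline value, region and previous use of biologics". ACR-N is tested by ANOVA without a baseline term (SAP 8.1.2). P-values versus placebo are Hommel-adjusted.

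SAP 4.4.3 also plans an observed-case analysis to gauge the effect of early dropout. Among continuous endpoints it is inferential only for ACR-N and DAS28(CRP), at Week 12. For SDAI and CDAI, SAP 8.3.2 specifies "LOCF and observed case (descriptive only"). Sections 8.5.2, 8.6.2, 8.7.2, 8.8.2, 8.9.2 and 8.10.2 set the same limit for joint counts, VAS, HAQ-DI, CRP, FACIT and SF-36. The general comments that open SAP section 8 are looser: they describe observed-case inference at Week 12 with no restriction by parameter. No mixed model, multiple imputation or other method valid under missing at random is planned.

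**The concern.** LOCF treats a subject who leaves at Week 4 as if the Week 4 score had been measured at Week 12. If scores are still improving at that point, the arm mean is pulled towards its earlier value, more so in the arm that loses more subjects or has more improvement left to lose. Unequal dropout is plausible here. Protocol 8.3.4 requires withdrawal for laboratory and infection findings, which could be dose-related. It also allows stopping for treatment failure, which could be commoner on placebo.

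What is at stake is the set of adjusted secondary p-values and differences versus placebo. Hommel's procedure protects the error rate only if the unadjusted p-values are valid. Several of these LOCF comparisons also go into the Week 12 interim tables that support preliminary phase III dose selection (SAP 6.2). A descriptive observed-case table gives some view of dropout, but it cannot show whether a test result depends on LOCF.

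**Working it through.** **1. The plan's own figure.** Protocol 8.8.2 gives "n=70 in each of the study arms, with a total of N=280 in the study, and" "Alpha = 5%/3 = 1.67% per comparison versus placebo, and" and "a 15% to 40% placebo ACR20 response at Week 12", and claims "90% power to detect a 28% (=43% - 15%) to 30% (=70% - 40%) treatment difference versus placebo". Sidedness is not stated; two-sided is assumed because it fits (one-sided gives 94.5% and 93.4%). For the pooled chi-square test:

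z = [|p2 - p1|·√n - 2.394·√(2·p̄·(1 - p̄))] / √(p1(1 - p1) + p2(1 - p2))

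- 15% vs 43%: (0.28·8.367 - 2.394·0.6417)/0.6104 = 1.32, power 90.7%.
- 40% vs 70%: (0.30·8.367 - 2.394·0.7036)/0.6708 = 1.23, power 89.1%.
- The 80% cases (15% vs 39%, 40% vs 67%) give 79.8% and 80.0%.

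The figures reproduce, but they concern ACR20 only. For continuous endpoints the documents supply n and alpha and nothing else.

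**2. Coverage.** Ten continuous endpoint families are tested on LOCF data. Two (ACR-N, DAS28) also have an observed-case test. Eight do not: SDAI 1 parameter, CDAI 1, joint counts 4, VAS 3, HAQ-DI 9, CRP 1, FACIT 1, SF-36 10. That is 30 of 32 parameters.

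**3. Closed form (assumed inputs).** Let μ be an arm's true Week 12 change, d its dropout share, and g the fraction of μ reached at the last observation. If dropout is unrelated to outcome, the LOCF arm mean is μ·[1 - d(1 - g)]. With a change of 1 on placebo and 2 on active (true difference 1.00):

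| Dropout placebo/active | g = 0 | g = 0.75 |
|---|---|---|
| 5%/20% | 2(0.80) - 0.95 = 0.65 | 2(0.95) - 0.9875 = 0.91 |
| 10%/10% | 2(0.90) - 0.90 = 0.90 | 2(0.975) - 0.975 = 0.98 |
| 20%/10% | 2(0.90) - 0.80 = 1.00 | 2(0.975) - 0.95 = 1.00 |
| 20%/5% | 2(0.95) - 0.80 = 1.10 | 2(0.9875) - 0.95 = 1.03 |

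So equal dropout attenuates, and unequal dropout can attenuate, inflate or cancel.

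On the DAS28 scale, take a placebo change of -1.00, active -1.60 and dropout 7%/18%. The LOCF difference is -0.60 + (1 - g)(0.18·1.60 - 0.07·1.00) = -0.60 + 0.218(1 - g). That is -0.49 at g = 0.50 and -0.55 at g = 0.75.

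**4. Simulation (all inputs assumed, 70 per arm).** First set: SD 1, visits to Week 12, no discontinuation visit, ANCOVA, 3,000 trials, true difference 1.00.

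| Dropout placebo/active | LOCF | Observed case | Missing-at-random estimate |
|---|---|---|---|
| about 8%/25%, unrelated to outcome | 0.784 | 1.000 | 0.999 |
| about 25%/8%, unrelated to outcome | 1.053 | 1.002 | 1.002 |
| about 10%/10%, unrelated to outcome | 0.948 | 0.998 | 0.999 |
| about 25%/18%, lack of efficacy | 0.935 | 0.983 | 1.005 |

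With no true difference and 5%/20% dropout, LOCF rejects 9.0% (both arms improve 1 SD) to 16.5% (both improve 2 SD) at a nominal 5%. Observed case rejects 5.4% and 5.3%.

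Second set: true DAS28 difference -0.60, alpha 1.67%.

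| Assumptions | LOCF at 7%/18% | Null rejection at 7%/24% |
|---|---|---|
| SD 1.2, dropout unrelated to outcome, no discontinuation visit | -0.47 to -0.54 | 1.9% to 6.6% |
| SD 1.2, dropout unrelated and uniform over Weeks 2-11 | -0.51 to -0.55; with a discontinuation visit -0.53 to -0.56 | 1.7% to 2.6% |
| Dropout depends on last observed change | -0.49 | 4.5% |

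Under lack-of-efficacy dropout of 29%/16%, LOCF gave -0.63, a slight overstatement. The first set's 25%/18% case gave shrinkage.

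**The case against.** The case on the other side is substantial, and much of it stands.

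- **The primary analysis is elsewhere.** The primary endpoint is ACR20 with non-responder imputation (SAP 6.1.2.1). A reader might infer that LOCF undermines the trial's main result or its dose comparison. The documents do not support that: only secondary endpoints are tested this way, and dose-versus-dose comparisons are unpowered and exploratory.
- **Safeguards exist.** Early leavers are to have a full efficacy assessment (Protocol 8.6.2.8), allocated by study day (SAP 3.3), so LOCF often carries the value at discontinuation. For endpoints measured from Week 1, carrying baseline should be rare, because the ITT set requires post-baseline efficacy data. It is likelier for FACIT and SF-36, first scheduled at Week 4. DAS28 has a per-protocol test, and SDAI/CDAI remission is tested with non-responder, LOCF and observed-case handling. These soften the problem, but none is a second test of the eight families on their own scale.
- **The sizes are assumed.** True. Milder assumptions leave the null rejection rate at nominal.
- **LOCF is in the protocol** (8.8.1.3), and the sponsor has viewed unblinded Week 12 summaries (SAP 6.2, 6.3.2). That argues against replacing the main analysis now. It does not argue against adding a second one.

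**Conclusion.** The gap is real: for eight of ten continuous endpoint families, LOCF is the only basis for inference. Given scores still changing at dropout, a true -0.60 at 7%/18% dropout becomes about -0.47 to -0.56. Null rejection at 7%/24% is about 1.7% to 6.6% at a nominal 1.67%. Dropout, SD, time course and the relation of dropout to outcome are all assumed. DAS28 serves only as the scale for illustration; it does have an observed-case test.

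Two stronger readings should be resisted. One is that the direction is known, for example that lack-of-efficacy dropout on placebo must inflate the effect. The two lack-of-efficacy simulations went opposite ways. Under the null with more dropout on active, the shift makes active look worse, so the excess rejections are not mainly false claims of benefit. The other is that an observed-case test would settle the matter: it is unbiased only when dropout is unrelated to outcome given the model.

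This is worth fixing, but it does not threaten the primary conclusion.

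**What to change.** Before final database lock, add to SAP 4.4.3 and 6.1.2.3 a likelihood-based MMRM without imputation, for every continuous endpoint to Week 12, reported beside the LOCF analysis:

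- Terms: treatment by visit, baseline by visit (omitted for ACR-N, which has no baseline value), region and prior biologics; unstructured covariance.
- Visits: Weeks 1, 2, 4, 8 and 12; Weeks 4 and 12 only for FACIT and SF-36.
- Week 12 contrasts versus placebo with the same Hommel adjustment.
- An explicit statement of the missing-at-random assumption.

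Record the addition in SAP 6.3.2, disclosing that unblinded interim summaries had already been seen. Reconcile the general observed-case comments opening SAP section 8 with SAP 4.4.3 and the parameter sections.

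The cost is SAP text and some extra programming and tables; no new data are needed. The added model relies on missing at random, which the data cannot verify, so agreement with LOCF would be reassuring rather than conclusive.
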